3.4 QUESTIONNAIRES

3.4.1 MD Anderson Symptom Inventory-Brain Tumor (MDASI-BT):

The MDASI-BT will be administered at baseline and at the time of imaging analysis as outlined in the protocol. Of note, every attempt should be made to administer the MDASI-BT prior to informing the patients about the results of the imaging study. The MDASI-BT will be completed only by the patient, unless changes in vision or weakness make this difficult. If this occurs, then the caregiver or research assistant may read the questions to the patient or assist with marking the severity number or score as described by the patient. A caregiver may complete the questionnaires as a patient proxy if the patient's deficits preclude self-report; however, this must be done at every assessment from baseline to end of treatment. In addition, information regarding demographics and treatment history will be collected as part of the larger study and used in this analysis.

The MDASI-BT consist of symptoms rated on an 11-point scale (0 to 10) to indicate the presence and severity of the symptom, with 0 being "not present" and 10 being "as bad as you can imagine." Each symptom is rated at its worst in the last 24 hours. Symptoms included on the instrument include those commonly associated with cancer therapies, and those associated with the underlying disease. The questionnaire also includes ratings of how much symptoms interfered with different aspects of a patient's life in the last 24 hours. These interference items include: general activity, mood, work (includes both work outside the home and housework), relations with other people, walking, and enjoyment of life. The interference items are also measured on 0 - 10 scales. The average time to complete this instrument is 5 minutes. The MDASI-BT has been translated into multiple languages, but the English language version will be used for this study[44].

3.4.2 PRO-CTCAE*:

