Early stop probability	0.014	0.096	0.345	0.716	0.939
Average sample size	39.6	37.3	31.0	21.3	13.5

At progression, patients on the control arm will be offered treatment with Zotiraciclib (TG02) in combination with continued treatment with TMZ. If an effective salvage regimen, this may impact the secondary OS endpoint, but will not affect the primary endpoint of the study. The maximum number is 80 patients.

Statistical Analysis Plan

We will use descriptive statistics to summarize the demographic and clinical characteristics of patients. We will tabulate adverse events by grade by dose level and overall. For the cohort expansion and phase II component, we will estimate the proportion of patients with response with 95% exact binomial confidence intervals, and use descriptive statistics to summarize response duration. We will estimate PFS/OS with the Kaplan-Meier product limit estimator. Log-rank test will be used to compare the PFS/OS between Zotiraciclib (TG02)+TMZ and TMZ.

Changes of symptom burden (i.e., MDASI-BT) through study time points will be assessed by paired t-tests and linear mixed model. In the mixed model, subject-specific random intercept will be used to account for within-subject correlation, and measurement time will be included as a covariate. A sample size of 40 patients has 80% power to detect an effect size of 0.454 between time points using a two-tailed test with an alpha of 0.05. The two-sample t-test and linear mixed model will be used to evaluate differences in symptom burden using the MDASI-BT between Zotiraciclib (TG02) plus TMZ and TMZ. Cox proportional hazard model will be used to evaluate the relationship between MDASI-BT and disease progression. Logistic regression will be used to evaluate the relationship between MDASI-BT and tolerance to treatment.

Treatment effects will be evaluated by advanced MRI imaging study. Perfusion and diffusion – based MRI parameters, including but not restricted to blood volume, blood flow mean and median Apparent Diffusion Coefficient (ADC) value will be analysed. Results will be summarized. The mean and median value at different time points will be tabulated. Changes in such parameters will be analysed for statistical significance and correlate with the disease status.

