10.2.1 Patient Reported Outcomes

Received MDASI-BT form will be checked versus the timing schedule and considered as valid if they fall within ten days of the scheduled assessment window. Compliance rates will be calculated as the number of received valid forms over the number of expected forms. Differences between groups in compliance will be tested by use of Fisher’s exact test at every time point.

We will use descriptive statistics to describe how patients rate symptom severity and interference with function at each time point. Error bar graphs for each of the symptoms will be constructed at each time point. The proportion of patients rating their symptoms to be 5 or greater (on a 0-10 scale) will also be reported. We will construct individual patient profiles for each of the selected symptoms to describe the individual patients’ patterns of change over time. We will calculate the mean symptom severity, and mean symptom interference at the time of clinical evaluation.

Estimates of differences in the mean symptom severity and mean symptom interference between responders and non-responders will be estimated in the intent to treat population. All patients

with at least one valid questionnaire will be included in the analyses. Questionnaires completed at study registration will be considered baseline. All questionnaire data received after randomization will be used in the primary analyses.

Differences of at least 2 points will be classified as the minimum clinically meaningful change in the symptom severity and symptom interference measures. For example, an increase of 2 points or more would mean a moderate improvement, whereas a decrease of 2 points or more would be interpreted as moderate worsening. For individual symptoms, a rise in a symptom score means deterioration, whereas a reduced score means improvement of the specific symptom.

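### Section 10.2.1 labels MDASI-BT change backwards: a rise of 2 or more points in severity or interference is called improvement, although higher scores are worse

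*Combined protocol and SAP*

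**What the plan says.** Section 3.4.1 describes the instrument. Each symptom is rated from 0 to 10; 0 means the symptom is absent and 10 means "as bad as you can imagine". The questionnaire also collects "ratings of how much symptoms interfered with different aspects of a" patient's life, and "The interference items are also measured on 0 - 10 scales". No item is said to be reverse-scored.

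Section 10.2.1 plans mean symptom severity and mean symptom interference as summary measures and sets the threshold: "Differences of at least 2 points will be classified as the minimum clinically meaningful change in the symptom severity and symptom interference measures". It illustrates the threshold by saying that "an increase of 2 points or more would mean a moderate improvement, whereas a decrease of 2 points or more would be interpreted" the opposite way, that is, as a worsening of moderate degree. The following sentence goes the other way: "For individual symptoms, a rise in a symptom score means deterioration", and a lower score is improvement. Earlier in the same section, high ratings are picked out for reporting: "The proportion of patients rating their symptoms to be 5 or greater (on a 0-10 scale) will also be reported".

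The Statistical Analysis Plan text in Section 10.2 gives the only computed figure for this endpoint: "A sample size of 40 patients has 80% power to detect an effect size of 0.454 between time points", two-tailed at alpha 0.05. Section 1.1.2 lists longitudinal MDASI-BT severity and interference as a secondary objective.

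**The concern.** The illustration reverses the direction of the scale. Whoever writes the results will look to this sentence for the words to attach to a change of 2 points or more, because the plan gives no other threshold for a clinically meaningful change. If they follow it, patients whose symptoms became worse are described as moderately improved, and the reverse. Section 1.2.8 justifies the questionnaire as a way to see both the positive and the negative impact of treatment, so direction is the one thing this rule has to get right.

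For individual symptoms the next sentence supplies the correct direction. For interference no such sentence exists, so the reversed illustration is the only direction that the analysis section states.

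**Working it through.** **1. Direction of the scale**

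| Source | Measure | What a higher score means |
|---|---|---|
| 3.4.1 | Symptom items | Worse (0 absent, 10 worst imaginable) |
| 3.4.1 | Interference items | More interference; inferred, since the end anchors are not spelled out |
| 10.2.1, illustration | Severity and interference measures | Improvement |
| 10.2.1, next sentence | Individual symptoms | Deterioration |

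The third row conflicts with the other three. The sentence about ratings of 5 or greater states no direction. It is only consistent with high scores being the troublesome ones.

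**2. Could the composite run opposite to its items?** Mean severity is planned as a plain mean, with no transformation described. For k items, if each rises by 2, the new mean is (Σxᵢ + 2k)/k = old mean + 2. For example, items 1, 2, 3, 4, 0, 5 have mean 15/6 = 2.5; adding 2 to each gives 27/6 = 4.5, a rise of 2.0. Mean severity therefore cannot improve because all its items deteriorate. The same holds for mean interference.

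**3. What the rule does to labels** (change = follow-up minus baseline)

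| Baseline | Follow-up | Change | 10.2.1 illustration | 3.4.1 scale |
|---|---|---|---|---|
| 2 | 4 | +2 | improvement | worsening |
| 3 | 5 | +2 | improvement | worsening |
| 5 | 3 | −2 | worsening | improvement |
| 6 | 4 | −2 | worsening | improvement |

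Every change of 2 points or more, in either direction, is mislabelled.

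**4. The plan's own power figure.** Inputs from Section 10.2: n = 40, standardised effect 0.454, two-sided alpha 0.05. For a paired t-test with 39 degrees of freedom, the noncentrality is 0.454 × √40 = 2.871. The exact noncentral-t power is 0.7996, and the normal approximation gives Φ(2.871 − 1.960) = 0.819. The stated 80% is reproduced. It comes from a two-sided test and does not depend on how a change is labelled.

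**5. Could the wrong label land on a statistically detectable change?** This is context only, because the contradiction does not depend on it. A mean change of 2 points equals 0.454 SD when the SD of change is 2/0.454 = 4.41. The documents give no SD, so the values below are assumed, with 40 complete pairs and noncentrality (2/SD) × √40:

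| Assumed SD of change | Noncentrality | Power for a 2-point mean change |
|---|---|---|
| 2 | 6.32 | >0.999 |
| 3 | 4.22 | 0.984 |
| 4 | 3.16 | 0.869 |
| 4.4 | 2.87 | 0.800 |
| 5 | 2.53 | 0.694 |

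**The case against.** The strongest reply is that this is an editorial slip with no analytic consequence. The sentence is introduced as an example. No planned analysis uses it: the paired and two-sample t-tests, the mixed models, the Cox and logistic models, the comparison of responders with non-responders, and the proportion at or above 5 all work from scores or a fixed cut. No tabulation of improved and worsened patients by arm is specified. Harm would need a writer to use a label that contradicts both Section 3.4.1 and the very next sentence. All of this stands, and it limits the point to interpretation.

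It can also be said that the next sentence covers individual symptoms while the illustration covers the summary measures, so the two need not conflict. That fails for severity, because the summary is the mean of those same items. For interference the conflict rests on the ordinary reading of a rating of how much symptoms interfered. That is an inference, though I see no other sensible reading.

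A last objection concerns the power table. It treats the 2 points as a change in a group mean, which the plan does not specify. It also assumes 40 complete pairs, which is optimistic: follow-up questionnaires come with imaging every two cycles, and Section 10.2 assumes a control median PFS of 3 months. That is fair. The table shows only that a mislabelled change could also be statistically significant; it does not measure the error.

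**Conclusion.** The concern holds. Section 10.2.1 states a direction for severity and interference that is the reverse of the scale in Section 3.4.1 and of its own next sentence, and no reverse scoring is described that would reconcile them. If the rule is followed as written, every change that meets the threshold is described with the wrong sign. For severity this follows directly from the stated anchors; for interference it follows by inference from what the items rate.

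The reach is narrow: wording and interpretation of one secondary objective. No test statistic, model estimate, p-value or power figure changes, and the primary PFS comparison is untouched. It should still be fixed, because this is the plan's only stated threshold for a clinically meaningful change in this endpoint.

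**What to change.** Replace the illustrative sentence in Section 10.2.1 with wording such as: *An increase of 2 points or more in symptom severity or symptom interference means moderate worsening, and a decrease of 2 points or more means moderate improvement. Higher scores are worse on every MDASI-BT item and on both means.*

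The cost is one exchanged pair of words and one added sentence, with no new data and no change to any test, model or sample size. While the text is open, it would help to say whether the 2 points refer to a patient's own change or to a difference in group means. That is a separate clarification, and the correction does not depend on it.

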11 COLLABORATIVE AGREEMENTS

11.1 AGREEMENT TYPE

The study agent, Zotiraciclib (TG02) is provided by Adastral Pharmaceuticals, Inc. under a Clinical Trials Agreement (CTA #01007-16). Results or study data may be communicated to CTA partner, Adastral Pharmaceuticals, Inc. according to the terms of the NIH- Advanced Accelerator Applications SA CTA. There is an executed Material Transfer Agreement (MTA#40216-15) with Adastral Pharmaceuticals.

12 HUMAN SUBJECTS PROTECTIONS

12.1 RATIONALE FOR SUBJECT SELECTION

This study was designed to include women and minorities but was not designed to measure differences of intervention effects. Males and females will be recruited with no preference to gender. No exclusion to this study will be based on race. Minorities will actively be recruited to participate.

12.2 PARTICIPATION OF CHILDREN

Because no dosing or adverse event data are currently available on the use of TMZ in combination with Zotiraciclib (TG02) in subjects <18 years of age, children are excluded from this study.

12.3 PARTICIPATION OF SUBJECTS UNABLE TO GIVE CONSENT

Adults unable to give consent are excluded from enrolling in the protocol. However, re-consent may be necessary and there is a possibility, though unlikely, that subjects could become decisionally impaired. For this reason and because there is a prospect of direct benefit from research participation (a potential for reduction in their tumor volume, which may or may not have favorable impact on symptoms and/or survival), all subjects will be offered the opportunity to fill in their wishes for research and care, and assign a substitute decision maker on the NIH Advance Directive for Health Care and Medical Research Participation” form so that another person can make decisions about their medical care in the event that they become incapacitated or cognitively impaired during the course of the study. Note: The PI or AI will contact the NIH Ability to Consent Assessment Team (ACAT) for evaluation as needed for the following: an independent assessment of whether an individual has the capacity to provide consent; assistance in identifying and assessing an appropriate surrogate when indicated; and/or an assessment of the

capacity to appoint a surrogate. For those subjects that become incapacitated and do not have pre-determined substitute decision maker, the procedures described in NIH HRPP SOP 14E for appointing a surrogate decision maker for adult subjects who are (a) decisionally impaired, and (b) who do not have a legal guardian or durable power of attorney, will be followed.

12.4 EVALUATION OF BENEFITS AND RISKS/DISCOMFORTS

12.4.1 The primary risk to patients participating in this research study is from toxicity of the Zotiraciclib (TG02) and TMZ as described in the protocol.

12.4.2 Alternative Approaches or Treatments

Patients will be consented verbally and in writing regarding the risks and benefits of this trial, the treatment requirements, and alternative approaches to entering on this trial.

12.4.3 Procedure for Protecting Against or Minimizing any Potential Risks

All care will be taken to minimize side effects, but they can be unpredictable in nature and severity. This study may involve risks to patients, which are currently unforeseeable. All patients will have blood tests, examinations and scans as described in the study calendar (Section 3.8). Patients will also be required to have a local physician to provide long-term care and to monitor for complications. If patients suffer any physical injury as a result of the participation in this study, immediate medical treatment is available at the Clinical Center, National Cancer Institute, Bethesda, Maryland. Although no compensation is available, any injury will be evaluated and treated in keeping with the benefits or care to which patients are entitled under applicable regulations.

12.4.4 Provisions for Monitoring Data Collection to Ensure Safety of Subjects

As information is gathered from this trial, clinical results will be shared with patients as they become available. Laboratory and clinical data will be frequently gathered and any new significant finding(s) found during the course of the research, which may affect a patient's willingness to participate further, will be explained. Confidentiality of information concerning participants will be maintained, including in all publications and presentations resulting from this study. Names of participants and/or material identifying participants will not be released without permission, except as such release is required by law. Records at the National Cancer Institute are maintained according to current legal requirements, and are made available for review, as required by the Food and Drug Administration or other authorized users, only under the guidelines established by the Federal Privacy Act.

12.5 RISKS/BENEFITS ANALYSIS

12.5.1 Benefits

The potential benefit to a patient on this study is a reduction in the bulk of their tumor and improvement in cancer lesions, which may or may not have favorable impact on symptoms and/or survival.

12.5.2 Risks

Risks include the possible occurrence of any of a range of side effects which are listed in the Consent Document or this protocol document. Frequent monitoring for adverse effects will help to minimize the risks associated with administration of the study agents.

12.5.3 MR Imaging with gadolinium

The MRIs to be done in this study will involve contrast. The risks associated with MRIs and contrast are discussed in the consent form.

Although MR imaging with gadolinium has been used as part of the standard care for patients with high grade gliomas, long term toxicities of gadolinium as a consequence of gadolinium accumulation in the body has been reported. All investigators will ascertain the MR imaging history of all prospective study participants to determine the extent of prior exposure to gadolinium contrast. Radiology will be consulted if there is a history of repeated gadolinium exposure.

12.5.4 Risks/Benefits Analysis

Given the potential benefits and the efforts to minimize risk with the administration of this combination, this protocol involves greater than minimal risk, but presents the potential for direct benefit to individual subjects, including those able to consent as well as those that may lose the capacity to do so over the course of the trial.

12.6 CONSENT AND ASSENT PROCESS AND DOCUMENTATION

The informed consent document will be provided to the participant for review prior to consenting. A designated study investigator will carefully explain the procedures and tests involved in this study, and the associated risks, discomforts and benefits. In order to minimize potential coercion, as much time as is needed to review the document will be given, including an opportunity to discuss it with friends, family members and/or other advisors, and to ask questions of any designated study investigator. A signed informed consent document will be obtained prior to entry onto the study.

12.6.1 The initial consent process as well as re-consent, when required, may take place in person or remotely (e.g., via telephone or other NIH approved remote platforms) per discretion of the designated study investigator and with the agreement of the participant/consent designee(s). Whether in person or remote, the privacy of the subject will be maintained. Consenting investigators (and participant/consent designee, when in person) will be located in a private area (e.g., clinic consult room). When consent is conducted remotely, the participant/consent designee will be informed of the private nature of the discussion and will be encouraged to relocate to a more private setting if needed. Request for Waiver of Consent for Screening Activities

Prior to the subject signing the consent for this study pre-screening activities listed in section [2.2.1 may be performed](#).

We request a waiver of consent for these activities as they involve only minimal risk to the subjects. A waiver will not adversely affect the rights and welfare of the subjects given that the

activities are only intended to determine suitability for screening for participation in research protocols. These activities could not practicably be carried out without the wavier as central recruiting services, utilized in the NIH Clinical Center, perform pre-screening activities for multiple studies and obtaining consent for each one is beyond their resources. The subjects will be provided with additional pertinent information after participation as they will be informed whether or not they are eligible to sign a consent for additional screening.

13 PHARMACEUTICAL INFORMATION

13.1 TEMOZOLOMIDE (TEMODAR®; METHAZOLASTONE)

For more information, please refer to the Package Insert.

13.1.1 Source

Temozolomide will be purchased from commercial sources to the NIH CC Pharmacy.

13.1.2 Formulation and preparation

Temozolomide Capsules are available in 5-mg, 20-mg, 100-mg, 140-mg, 180-mg, and 250- mg strengths. The capsules contain a white capsule body with a color cap, and the colors vary based on the dosage strength.

Each strength of TEMODAR must be dispensed in a separate vial or in its original package (one strength per one container). Follow the instructions below: Based on the dose prescribed, determine the number of each strength of TEMODAR capsules that are needed. Label each container with the appropriate number of capsules to be taken each day. Dispense to the patient, making sure each container lists the strength (mg) per capsule and that he or she understands to take the appropriate number of capsules of TEMODAR from each package or vial to equal the total daily dose prescribed by the physician. TEMODAR is store at 25°C, excursions permitted to 15-30°C.

13.1.3 Contraindications

There are no dietary restrictions for patients taking TEMODAR. TEMODAR may affect testicular function, so male patients should exercise adequate birth control measures. TEMODAR may cause birth defects. Female patients should avoid becoming pregnant while receiving this drug. Women who are nursing prior to receiving TEMODAR should discontinue nursing. It is not known whether TEMODAR is excreted into breast milk. Because many drugs are excreted in human milk, and because of the potential for serious adverse reactions in nursing infants and tumorigenicity shown for temozolomide in animal studies, a decision should be made whether to discontinue nursing or to discontinue the drug, taking into account the importance of TEMODAR to the mother.

